9.6.2. Imputation of Missing Not at Random (MNAR) Cases

The MNAR cases are imputed using reference based imputation (J2R) method. The five macros; SAS code for reference based multiple imputation [<https://www.lshtm.ac.uk/research/centres-projects-groups/missing-data#dia-working-group>] will be used to generate 27 possible imputed datasets using the following sample SAS code:

```
%include "&Path\part1A_33.sas";
%include "&Path\part1B_47.sas";
%include "&Path\part2A_40.sas";
%include "&Path\part2B_31.sas";
%include "&Path\part3_55.sas";
%include "&Path\plotter_7.sas";

%part1a(Jobname=X, Data=XX, Subject=usubjid, Response=aval, Time=avisitn, Treat=Trt01pn, cov=BASE, Catcov=MAOBINHI, covgroup=trt01pn, Debug=1);
%part1b(Jobname=X, Ndraws=27, thin=350, seed=s, Debug=1);

%part2a(Jobname=X_J2R, inname=XX, method=J2R, ref=0, Debug=1);
%part2b(Jobname=X_J2R, seed=s, Debug=1);
```

Each of these datasets will be analyzed using PROC MIXED in SAS using the MMRM model. The results of the analyses of the datasets will be combined using PROC MIANALYZE to produce an inferential result.

9.8. CTCAE Based Laboratory Test Results Grading Specifications

Lab Test = Albumin

CTCAE Term	Grade 1	Grade 2	Grade 3	Grade 4	Grade 5
Hypoalbuminemia	<LLN - 3 g/dL; <LLN - 30 g/L	<3 - 2 g/dL; <30 - 20 g/L	<2 g/dL; <20 g/L	Life-threatening consequences; urgent intervention indicated	Death

Albumin will have grades 1-3,

- Grade 1 being any values from the LLN to 3 g/dL,
- Grade 2 from 2 to < 3 g/dL and
- Grade 3 < 2 g/dL

Lab Test = Amylase

CTCAE Term	Grade 1	Grade 2	Grade 3	Grade 4	Grade 5
Serum amylase increased	>ULN - 1.5 x ULN	>1.5 - 2.0 x ULN; >2.0 - 5.0 x ULN and asymptomatic	>2.0 - 5.0 x ULN with signs or symptoms; >5.0 x ULN and asymptomatic	>5.0 x ULN and with signs or symptoms	-

Amylase will have Grades 1, 2 and 3:

- Grade 1 being any values from the ULN to 1.5 x ULN
- Grade 2 from >1.5 to 5.0 x ULN
- Grade 3 from >5 x ULN

Lab Test = Alkaline Phosphatase

CTCAE Term	Grade 1	Grade 2	Grade 3	Grade 4	Grade 5
Alkaline phosphatase increased	>ULN - 2.5 x ULN if baseline was normal; 2.0 - 2.5 x baseline if baseline was abnormal	>2.5 - 5.0 x ULN if baseline was normal; >2.5 - 5.0 x baseline if baseline was abnormal	>5.0 - 20.0 x ULN if baseline was normal; >5.0 - 20.0 x baseline if baseline was abnormal	>20.0 x ULN if baseline was normal; >20.0 x baseline if baseline was abnormal	-

Alkaline Phosphatase will have grades 1-4 and grading is based ULN only.

- Grade 1 being any values from the ULN to 2.5 x ULN
- Grade 2 from >2.5 to 5.0 x ULN
- Grade 3 from >5.0 to 20.0 x ULN
- Grade 4 from >20.0 x ULN

Lab Test = Alanine Aminotransferase

CTCAE Term	Grade 1	Grade 2	Grade 3	Grade 4	Grade 5
Alanine aminotransferase increased	>ULN - 3.0 x ULN if baseline was normal; 1.5 - 3.0 x baseline if baseline was abnormal	>3.0 - 5.0 x ULN if baseline was normal; >3.0 - 5.0 x baseline if baseline was abnormal	>5.0 - 20.0 x ULN if baseline was normal; >5.0 - 20.0 x baseline if baseline was abnormal	>20.0 x ULN if baseline was normal; >20.0 x baseline if baseline was abnormal	-

ALT will have grades 1-4 and grading is based ULN only.

- Grade 1 being any values from the ULN to 3.0 x ULN
- Grade 2 from >3.0 to 5.0 x ULN
- Grade 3 from >5.0 to 20.0 x ULN
- Grade 4 from >20.0 x ULN

Lab Test = Aspartate Aminotransferase

CTCAE Term	Grade 1	Grade 2	Grade 3	Grade 4	Grade 5
Aspartate aminotransferase increased	>ULN - 3.0 x ULN if baseline was normal; 1.5 - 3.0 x baseline if baseline was abnormal	>3.0 - 5.0 x ULN if baseline was normal; >3.0 - 5.0 x baseline if baseline was abnormal	>5.0 - 20.0 x ULN if baseline was normal; >5.0 - 20.0 x baseline if baseline was abnormal	>20.0 x ULN if baseline was normal; >20.0 x baseline if baseline was abnormal	-

AST will have grades 1-4 and grading is based ULN only.

- Grade 1 being any values from the ULN to 3.0 x ULN
- Grade 2 from >3.0 to 5.0 x ULN
- Grade 3 from >5.0 to 20.0 x ULN
- Grade 4 from >20.0 x ULN

Lab Test = Bilirubin

CTCAE Term	Grade 1	Grade 2	Grade 3	Grade 4	Grade 5
Blood bilirubin increased	>ULN - 1.5 x ULN if baseline was normal; > 1.0 - 1.5 x baseline if baseline was abnormal	>1.5 - 3.0 x ULN if baseline was normal; >1.5 - 3.0 x baseline if baseline was abnormal	>3.0 - 10.0 x ULN if baseline was normal; >3.0 - 10.0 x baseline if baseline was abnormal	>10.0 x ULN if baseline was normal; >10.0 x baseline if baseline was abnormal	-

Bilirubin will have grades 1-4 and grading is based ULN only

- Grade 1 being any values from the ULN to 1.5 x ULN
- Grade 2 from >1.5 to 3.0 x ULN
- Grade 3 from >3.0 to 10.0 x ULN
- Grade 4 from >10.0 x ULN

Lab Test = Corrected Serum Calcium

CTCAE Term	Grade 1	Grade 2	Grade 3	Grade 4	Grade 5
Hypocalcemia	Corrected serum calcium of <LLN - 8.0 mg/dL; <LLN - 2.0 mmol/L; Ionized calcium <LLN - 1.0 mmol/L	Corrected serum calcium of <8.0 - 7.0 mg/dL; <2.0 - 1.75 mmol/L; Ionized calcium <1.0 - 0.9 mmol/L; symptomatic	Corrected serum calcium of <7.0 - 6.0 mg/dL; <1.75 - 1.5 mmol/L; Ionized calcium <0.9 - 0.8 mmol/L; hospitalization indicated	Corrected serum calcium of <6.0 mg/dL; <1.5 mmol/L; Ionized calcium <0.8 mmol/L; life-threatening consequences	Death
Hypercalcemia	Corrected serum calcium of >ULN - 11.5 mg/dL; >ULN - 2.9 mmol/L; Ionized calcium >ULN - 1.5 mmol/L	Corrected serum calcium of >11.5 - 12.5 mg/dL; >2.9 - 3.1 mmol/L; Ionized calcium >1.5 - 1.6 mmol/L; symptomatic	Corrected serum calcium of >12.5 - 13.5 mg/dL; >3.1 - 3.4 mmol/L; Ionized calcium >1.6 - 1.8 mmol/L; hospitalization indicated	Corrected serum calcium of >13.5 mg/dL; >3.4 mmol/L; Ionized calcium >1.8 mmol/L; life-threatening consequences	Death

Calcium will have to be corrected for albumin using Payne's formula:

Corrected calcium = measured Ca (mg/dL) + 0.8 × (4.0 g/dL – patient albumin (g/dL)).

(NOTE: It should be confirmed with the lab whether or not the correction has already been applied).

The grading is in both directions High and Low. Both directions are graded in 4 categories as

Hypercalcemia

- Grade 1 being any values from the ULN to 11.5 mg/dL,
- Grade 2 from >11.5 to 12.5 mg/dL,
- Grade 3 from >12.5 to 13.5 mg/dL,
- Grade 4 >13.5 mg/dL

Hypocalcemia

- Grade 1 being any values from the LLN to 8.0 mg/dL,
- Grade 2 from 7.0 to <8.0 mg/dL,
- Grade 3 from 6.0 to <7.0 mg/dL,
- Grade 4 <6.0 mg/dL

Lab Test = Cholesterol

CTCAE Term	Grade 1	Grade 2	Grade 3	Grade 4	Grade 5
Cholesterol high	>ULN - 300 mg/dL; >ULN - 7.75 mmol/L	>300 - 400 mg/dL; >7.75 - 10.34 mmol/L	>400 - 500 mg/dL; >10.34 - 12.92 mmol/L	>500 mg/dL; >12.92 mmol/L	-

Cholesterol will have grades 1-4,

- Grade 1 being any values from the ULN to 300 mg/dL,
- Grade 2 from >300 to 400 mg/dL,
- Grade 3 from >400 to 500 mg/dL,
- Grade 4 >500 mg/dL

Lab Test = Creatine Kinase

CTCAE Term	Grade 1	Grade 2	Grade 3	Grade 4	Grade 5
CPK increased	>ULN - 2.5 x ULN	>2.5 x ULN - 5 x ULN	>5 x ULN - 10 x ULN	>10 x ULN	-

Creatine Kinase will have grades 1-4,

- Grade 1 being any values from the ULN to 2.5 x ULN ,
- Grade 2 from >2.5 to 5 x ULN ,
- Grade 3 from >5 to 10 x ULN ,
- Grade 4 >10 ULN

Lab Test = Creatinine

CTCAE Term	Grade 1	Grade 2	Grade 3	Grade 4	Grade 5
Creatinine increased	>ULN - 1.5 x ULN	>1.5 - 3.0 x baseline; >1.5 - 3.0 x ULN	>3.0 x baseline; >3.0 - 6.0 x ULN	>6.0 x ULN	-

Creatinine will have grades 1-4

- Grade 1 being any values from the ULN to 1.5 x ULN ,
- Grade 2 from >1.5 to 3.0 x ULN or >1.5 - 3.0 x baseline ,
- Grade 3 from >3.0 to 6.0 x ULN or >3.0 x baseline ,
- Grade 4 >6.0 x ULN

Lab Test = Fibrinogen

CTCAE Term	Grade 1	Grade 2	Grade 3	Grade 4	Grade 5
Fibrinogen decreased	<1.0 - 0.75 x LLN; if abnormal, <25% decrease from baseline	<0.75 - 0.5 x LLN; if abnormal, 25 - <50% decrease from baseline	<0.5 - 0.25 x LLN; if abnormal, 50 - <75% decrease from baseline	<0.25 x LLN; if abnormal, 75% decrease from baseline; absolute value <50 mg/dL	-

Fibrinogen will have Grades 1- 4:

- Grade 1 <1.0 - 0.75 x LLN
- Grade 2 <0.75 - 0.5 x LLN
- Grade 3 <0.5 - 0.25 x LLN
- Grade 4 <0.25 x LLN

Lab Test = Gamma-Glutamyl Transpeptidase

CTCAE Term	Grade 1	Grade 2	Grade 3	Grade 4	Grade 5
GGT increased	>ULN - 2.5 x ULN if baseline was normal; 2.0 - 2.5 x baseline if baseline was abnormal	>2.5 - 5.0 x ULN if baseline was normal; >2.5 - 5.0 x baseline if baseline was abnormal	>5.0 - 20.0 x ULN if baseline was normal; >5.0 - 20.0 x baseline if baseline was abnormal	>20.0 x ULN if baseline was normal; >20.0 x baseline if baseline was abnormal	-

Gamma-Glutamyl Transpeptidase will have grades 1-4 and based on ULN only

- Grade 1 being any values from the ULN to 2.5 x ULN,
- Grade 2 from >2.5 to 5.0 x ULN
- Grade 3 from >5.0 to 20.0 x ULN
- Grade 4 from >20.0 x ULN

Lab Test = Glucose

CTCAE Term	Grade 1	Grade 2	Grade 3	Grade 4	Grade 5
Hyperglycemia	Abnormal glucose above baseline with no medical intervention	Change in daily management from baseline for a diabetic; oral antiglycemic agent initiated; workup for diabetes	Insulin therapy initiated; hospitalization indicated	Life-threatening consequences; urgent intervention indicated	Death
Hypoglycemia	<LLN - 55 mg/dL; <LLN - 3.0 mmol/L	<55 - 40 mg/dL; <3.0 - 2.2 mmol/L	<40 - 30 mg/dL; <2.2 - 1.7 mmol/L	<30 mg/dL; <1.7 mmol/L; life-threatening consequences; seizures	Death

Hypoglycemia will have grades 1-4,

- Grade 1 being any values from the LLN to 55 mg/dL,
- Grade 2 from 40 to <55 mg/dL,
- Grade 3 from 30 to <40 mg/dL,
- Grade 4 <30 mg/dL

Hyperglycemia will have one grade using the WHO criterion below

- Grade 1 >200 mg/dL;

Lab Test = Lipase

CTCAE Term	Grade 1	Grade 2	Grade 3	Grade 4	Grade 5
Serum lipase increased	>ULN - 1.5 x ULN	>1.5 - 2.0 x ULN; >2.0 - 5.0 x ULN and asymptomatic	>2.0 - 5.0 x ULN with signs or symptoms; >5.0 x ULN and asymptomatic	>5.0 x ULN and with signs or symptoms	-

Lipase will have Grades 1, 2 and 3:

- Grade 1 being any values from the ULN to 1.5 x ULN
- Grade 2 from >1.5 to 5.0 x ULN
- Grade 3 from >5 x ULN

Lab Test = Magnesium

CTCAE Term	Grade 1	Grade 2	Grade 3	Grade 4	Grade 5
Hypermagnesemia	>ULN - 3.0 mg/dL; >ULN - 1.23 mmol/L	-	>3.0 - 8.0 mg/dL; >1.23 - 3.30 mmol/L	>8.0 mg/dL; >3.30 mmol/L; life-threatening consequences	Death
Hypomagnesemia	<LLN - 1.2 mg/dL; <LLN - 0.5 mmol/L	<1.2 - 0.9 mg/dL; <0.5 - 0.4 mmol/L	<0.9 - 0.7 mg/dL; <0.4 - 0.3 mmol/L	<0.7 mg/dL; <0.3 mmol/L; life-threatening consequences	Death

Hypermagnesemia will have grades 1, 3, and 4,

- Grade 1 being any values from the ULN to 3.0 mg/dL,
- Grade 3 from >3.0 to 8.0 mg/dL,
- Grade 4 from >8.0 mg/dL

Hypomagnesemia will have grades 1 - 4,

- Grade 1 being any values from the LLN to 1.2 mg/dL,
- Grade 2 from 0.9 to <1.2 mg/dL,
- Grade 3 from 0.7 to <0.9 mg/dL,
- Grade 4 <0.7 mg/dL

Lab Test = Potassium

CTCAE Term	Grade 1	Grade 2	Grade 3	Grade 4	Grade 5
Hyperkalemia	>ULN - 5.5 mmol/L	>5.5 - 6.0 mmol/L; intervention initiated	>6.0 - 7.0 mmol/L; hospitalization indicated	>7.0 mmol/L; life-threatening consequences	Death
Hypokalemia	<LLN - 3.0 mmol/L	Symptomatic with <LLN - 3.0 mmol/L; intervention indicated	<3.0 - 2.5 mmol/L; hospitalization indicated	<2.5 mmol/L; life-threatening consequences	Death

Hyperkalemia will have grades 1-4,

- Grade 1 being any values from the ULN to 5.5 mmol/L,
- Grade 2 from >5.5 to 6.0 mmol/L,
- Grade 3 from >6.0 to 7.0 mmol/L,
- Grade 4 from >7.0 mmol/L

Hypokalemia will have grades 1, 3, and 4,

- Grade 1 being any values from the LLN to 3.0 mmol/L,
- Grade 3 from >2.5 to 3.0 mmol/L,
- Grade 4 <2.5 mmol/L

Lab Test = Sodium

CTCAE Term	Grade 1	Grade 2	Grade 3	Grade 4	Grade 5
Hypernatremia	>ULN - 150 mmol/L	>150 - 155 mmol/L; intervention initiated	>155 - 160 mmol/L; hospitalization indicated	>160 mmol/L; life-threatening consequences	Death
Hyponatremia	<LLN - 130 mmol/L	125-129 mmol/L and asymptomatic	125-129 mmol/L symptomatic; 120-124 mmol/L regardless of symptoms	<120 mmol/L; life-threatening consequences	Death

Hypernatremia will have grades 1-4,

- Grade 1 being any values from the ULN to 150 mmol/L,
- Grade 2 from >150 to 155 mmol/L,
- Grade 3 from >155 to 160 mmol/L,
- Grade 4 from >160 mmol/L

Hyponatremia will have grades 1-4,

- Grade 1 being any values from the LLN to 130 mmol/L,
- Grade 2 from 125 to <130 mmol/L,
- Grade 3 from 120 to <125 mmol/L,
- Grade 4 <120 mmol/L

Lab Test = Triglycerides

CTCAE Term	Grade 1	Grade 2	Grade 3	Grade 4	Grade 5
Hypertriglyceridemia	150 mg/dL - 300 mg/dL; 1.71 mmol/L - 3.42 mmol/L	>300 mg/dL - 500 mg/dL; >3.42 mmol/L - 5.7 mmol/L	>500 mg/dL - 1000 mg/dL; >5.7 mmol/L - 11.4 mmol/L	>1000 mg/dL; >11.4 mmol/L; life-threatening consequences	Death

Triglycerides will have grades 1-4,

- Grade 1 being any values from the 150 to 300 mg/dL,
- Grade 2 from >300 to 500 mg/dL,
- Grade 3 from >500 to 1000 mg/dL,
- Grade 4 from >1000 mg/dL

Lab Test = Uric Acid

CTCAE Term	Grade 1	Grade 2	Grade 3	Grade 4	Grade 5
Hyperuricemia	>ULN without physiologic consequences	-	>ULN with physiologic consequences	Life-threatening consequences	Death

Uric Acid will not be CTCAE graded.

Lab Test = Bicarbonate or CO₂

CTCAE Term	Grade 1	Grade 2	Grade 3	Grade 4	Grade 5
Blood bicarbonate decreased	<LLN and no intervention initiated	-	-	-	-

Bicarbonate or CO₂ will not be CTCAE graded.

Lab Test = Phosphorus or Phosphate

CTCAE Term	Grade 1	Grade 2	Grade 3	Grade 4	Grade 5
Hypophosphatemia	Laboratory finding only and intervention not indicated	Oral replacement therapy indicated	Severe or medically significant but not immediately life-threatening; hospitalization or prolongation of existing hospitalization indicated	Life-threatening consequences	Death
Hyperphosphatemia	Laboratory finding only and intervention not indicated	Noninvasive intervention indicated	Severe or medically significant but not immediately life-threatening; hospitalization or prolongation of existing hospitalization indicated	Life-threatening consequences; urgent intervention indicated (e.g., dialysis)	Death

Phosphorus or Phosphate will not be CTCAE graded.

Lab Test = Serum pH [This is not urine pH]

CTCAE Term	Grade 1	Grade 2	Grade 3	Grade 4	Grade 5
Acidosis	pH <normal, but ≥7.3	-	pH <7.3	Life-threatening consequences	-
Alkalosis	pH >normal, but ≤7.5	-	pH >7.5	Life-threatening consequences	-

Serum pH will be graded in both directions with Grades 1 and 3 only.

Acidosis Grade 1 .<LLN, but ≥7.3 Grade 3, pH < 7.3

Alkaosis Grade 1 .>ULN, but ≤7.5 Grade 3, pH < 7.5

Lab Test = Activated Partial Thromboplastin Time

CTCAE Term	Grade 1	Grade 2	Grade 3	Grade 4	Grade 5
Activated partial thromboplastin time prolonged	>ULN - 1.5 x ULN	>1.5 - 2.5 x ULN	>2.5 x ULN; bleeding	-	-

APTT will be graded in Grade 1-3

- Grade 1 being any values from the >ULN to 1.5 x ULN,
- Grade 2 from >1.5 to 2.5 x ULN,
- Grade 3 from >2.5 x ULN,

Lab Test = International Normalized Ratio

CTCAE Term	Grade 1	Grade 2	Grade 3	Grade 4	Grade 5
INR increased	>1.2 - 1.5; >1 - 1.5 x baseline if on anticoagulation; monitoring only indicated	>1.5 - 2.5; >1.5 - 2.5 x baseline if on anticoagulation; dose adjustment indicated	>2.5; >2.5 x baseline if on anticoagulation; bleeding	-	-

INR will be graded in Grade 1-3 without baseline factor

- Grade 1 being any values from the >1.2 to 1.5,
- Grade 2 from >1.5 to 2.5,
- Grade 3 from >2.5,

Lab Test = Eosinophils

CTCAE Term	Grade 1	Grade 2	Grade 3	Grade 4	Grade 5
Eosinophilia	>ULN and >Baseline	-	Steroids initiated	-	-

Eosinophils will not be CTCAE graded

Lab Test = Hemoglobin

CTCAE Term	Grade 1	Grade 2	Grade 3	Grade 4	Grade 5
Anemia	Hemoglobin (Hgb) <LLN - 10.0 g/dL; <LLN - 6.2 mmol/L; <LLN - 100 g/L	Hgb <10.0 - 8.0 g/dL; <6.2 - 4.9 mmol/L; <100 - 80g/L	Hgb <8.0 g/dL; <4.9 mmol/L; <80 g/L; transfusion indicated	Life-threatening consequences; urgent intervention indicated	Death
Hemoglobin Increased	Increase in > 0-2	Increase in >2-4g/dL	Increase > 4 g/DL	-	Death

Decreased Hemoglobin will have grades 1-3, with

- Grade 1 being any values from the LLN to 10 g/DL,
- Grade 2 from 8 to < 10 g/DL and
- Grade 3 < 8 g/DL

Increased Hemoglobin will not be graded.

Lab Test = CD4 Lymphocytes

CTCAE Term	Grade 1	Grade 2	Grade 3	Grade 4	Grade 5
CD4 lymphocytes decreased	<LLN - 500/mm ³ ; <LLN - 0.5 x 10 ⁹ /L	<500 - 200/mm ³ ; <0.5 - 0.2 x 10 ⁹ /L	<200 - 50/mm ³ ; <0.2 x 0.05 - 10 ⁹ /L	<50/mm ³ ; <0.05 x 10 ⁹ /L	-

Decreased CD4 count will have grades 1-4, with

- Grade 1 being any values from the LLN to 500/mm³,
- Grade 2 from <500 to 200/mm³ and
- Grade 3 from <200 to 50/mm³ and
- Grade 4 <50/mm³

Lab Test = Lymphocytes

CTCAE Term	Grade 1	Grade 2	Grade 3	Grade 4	Grade 5
Lymphocyte count decreased	<LLN - 800/mm ³ ; <LLN - 0.8 x 10 ⁹ /L	<800 - 500/mm ³ ; <0.8 - 0.5 x 10 ⁹ /L	<500 - 200/mm ³ ; <0.5 - 0.2 x 10 ⁹ /L	<200/mm ³ ; <0.2 x 10 ⁹ /L	Lymphocyte count decreased
Lymphocyte count increased	-	>4000/mm ³ - 20,000/mm ³	>20,000/mm ³	-	Lymphocyte count increased

Decreased Lymphocytes will have grades 1-4, with

- Grade 1 being any values from the LLN to 800/mm³,
- Grade 2 from <800 to 500/mm³ and
- Grade 3 from <500 to 200/mm³ and
- Grade 4 <200/mm³

Increase Lymphocytes will have grades 2 and 3 only, with

- Grade 2 from >4000 to 20,000/mm³ and
- Grade 3 >20,000/mm³

Lab Test = Neutrophils

CTCAE Term	Grade 1	Grade 2	Grade 3	Grade 4	Grade 5
Neutrophil count decreased	<LLN - 1500/mm ³ ; <LLN - 1.5 x 10 ⁹ /L	<1500 - 1000/mm ³ ; <1.5 - 1.0 x 10 ⁹ /L	<1000 - 500/mm ³ ; <1.0 - 0.5 x 10 ⁹ /L	<500/mm ³ ; <0.5 x 10 ⁹ /L	-

Neutrophils will have grades 1-4, with

- Grade 1 being any values from the LLN to 1500/mm³,
- Grade 2 from 1000 to <1500/mm³ and
- Grade 3 from 500 to <1000/mm³ and
- Grade 4 <500/mm³

Lab Test = Platelets

CTCAE Term	Grade 1	Grade 2	Grade 3	Grade 4	Grade 5
Platelet count decreased	<LLN - 75,000/mm ³ ; <LLN - 75.0 x 10 ⁹ /L	<75,000 - 50,000/mm ³ ; <75.0 - 50.0 x 10 ⁹ /L	<50,000 - 25,000/mm ³ ; <50.0 - 25.0 x 10 ⁹ /L	<25,000/mm ³ ; <25.0 x 10 ⁹ /L	-

Platelet count will not be CTCAE graded

Lab Test = WBC

CTCAE Term	Grade 1	Grade 2	Grade 3	Grade 4	Grade 5
White blood cell decreased	<LLN - 3000/mm3; <LLN - 3.0 x 10e9 /L	<3000 - 2000/mm3; <3.0 - 2.0 x 10e9 /L	<2000 - 1000/mm3; <2.0 - 1.0 x 10e9 /L	<1000/mm3; <1.0 x 10e9 /L	-
Leukocytosis	-	-	>100,000/mm3	Clinical manifestations of leucostasis; urgent intervention indicated	Death

Decreased WBC will have grades 1-4, with

- Grade 1 being any values from the LLN to 3000/mm3,
- Grade 2 from 2000 to <3,000/mm3 and
- Grade 3 from 1000 to <2,000/mm3 and
- Grade 4 <1000/mm3

High WBC will have grade 1, with

- Grade 1 >11,000/mm3 (<https://www.aafp.org/afp/2000/1101/p2053.html>),

Lab Test = Urine Glucose

CTCAE Term	Grade 1	Grade 2	Grade 3	Grade 4	Grade 5
Glucosuria	Present	-	-	-	-

Urine Glucose will have grades 1,

- Grade 1 if not negative or trace

Lab Test = Urine Protein

CTCAE Term	Grade 1	Grade 2	Grade 3	Grade 4	Grade 5
Proteinuria	1+ proteinuria; urinary protein \geq ULN - <1.0 g/24 hrs	Adult: 2+ and 3+ proteinuria; urinary protein 1.0 - <3.5 g/24 hrs; Pediatric: Urine P/C (Protein/Creatinine) ratio 0.5 - 1.9	Adult: Urinary protein \geq 3.5 g/24 hrs; 4+ proteinuria; Pediatric: Urine P/C (Protein/Creatinine) ratio $>$ 1.9	-	-

Urine Protein will have grades 1-3, with

- Grade 1 =1+,
- Grade 2 = 2+ to 3+
- Grade 3 = 4+

Lab Test: Urine RBCs/Blood

CTCAE Term	Grade 1	Grade 2		Grade 3	Grade 4	Grade 5
Hematuria	Asymptomatic; clinical or diagnostic observations only; intervention not indicated	Symptomatic; urinary catheter or bladder irrigation indicated; limiting instrumental ADL		Gross hematuria; transfusion, IV medications, or hospitalization indicated; elective invasive intervention indicated; limiting self care ADL	Life-threatening consequences; urgent invasive intervention indicated	Death

Urine blood will not be CTCAE graded

Lab Test: eGFR or CrCl

CTCAE Term	Grade 1	Grade 2	Grade 3	Grade 4	Grade 5
eGFR decreased/CrCl decreased	eGFR (estimated Glomerular Filtration Rate) or CrCl (creatinine clearance) <LLN - 60 ml/min/1.73 m ² or proteinuria 2+ present; urine protein/creatinine >0.5	eGFR or CrCl 59 - 30 ml/min/1.73 m ²	eGFR or CrCl 29 - 15 ml/min/1.73 m ²	eGFR or CrCl <15 ml/min/1.73 m ² ; dialysis or renal transplant indicated	Death

Values will be graded using the CTCAE values noted above with Grade 1 – Grade 4 values.

eGFR/CrCl:

Grade 1: < LLN – 60 ml/min/1.73 m²

Grade 2: 30 - < 60 ml/min/1.73 m²

Grade 3: 15 - < 30 ml/min/1.73 m²

Grade 4: < 15 ml/min/1.73

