5.14.5. Clinical Laboratory Assessments

Descriptive summaries of selected (quantitative) clinical laboratory results will be presented by treatment group and study visit. Laboratory values outside the normal range for each systematically collected hematology, blood chemistry, and urinalysis parameter will be identified. Each subject's hematology, blood chemistry, and quantitative urinalysis values will be flagged as "low" (below the lower limit of normal/LLN), "normal" (within the normal range), or "high" (above the upper limit of normal/ULN) relative to the normal ranges of the central laboratory. Each subject's qualitative urinalysis results will be flagged as "normal" or "abnormal". In addition, the severity of laboratory abnormality will be graded based on toxicity criteria specified in [Section 9.8](#) in reference to Common Terminology Criteria for Adverse Events (CTCAE) Version 5.0. The result of each laboratory test for individual subjects will be presented in a listing with the normal range defined by the central laboratory, the status relative to the normal range, and the toxicity grade.

Shift table will be used to summarize shifts from baseline toxicity grades to greatest (worst) treatment-emergent laboratory toxicity grade. For hematology and, blood chemistry, and quantitative urinalysis parameters that toxicity grade was not defined, a shift table for each laboratory test will be based on the shift from baseline high/normal/low status to the status of the maximum post-baseline value and the minimum post-baseline value (including test results from unscheduled visits, if any). Similarly, for qualitative urinalysis parameters, shifts from baseline normal/abnormal status to the worst post-baseline status will be summarized.

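### SAP 5.14.5 gives a high/normal/low shift table only to ungraded tests, so a rise in glucose from normal to between the ULN and 200 mg/dL is tabulated as no change (on a literal reading, so are high hemoglobin and neutrophils)

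*SAP*

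**What the plan says.** SAP 5.14.5 plans two kinds of laboratory shift table. The first works on grades: "Shift table will be used to summarize shifts from baseline toxicity grades to greatest (worst) treatment-emergent laboratory toxicity grade". The second is conditional and covers only some of the hematology, chemistry and quantitative urinalysis tests. Its condition reads: "parameters that toxicity grade was not defined, a shift table for each laboratory test will be based on the shift from baseline high/normal/low status". The comparison is with the status of the highest and of the lowest value after baseline.

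SAP 9.8 decides which tests have a grade:

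- **Glucose.** On the low side, "Hypoglycemia will have grades 1-4". On the high side, "Hyperglycemia will have one grade using the WHO criterion below", and that criterion is "Grade 1 >200 mg/dL". The CTCAE row printed above it begins lower, at "Abnormal glucose above baseline with no medical intervention".
- **Hemoglobin.** "Decreased Hemoglobin will have grades 1-3, with" cut-offs running down from the lower limit of normal (LLN). For the other direction, "Increased Hemoglobin will not be graded".
- **Neutrophils.** Four grades, all for low counts, and nothing for high counts.
- **Platelets and eosinophils.** Not graded at all.

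SAP 3.2.4.1 separates two concepts. A treatment-emergent abnormality is any on-treatment value outside the normal range. A treatment-emergent toxicity needs a rise of at least one grade.

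**The concern.** The condition for the high/normal/low table is whether the test has a grade, not whether the grades cover all of its abnormal values. A test graded over only part of its abnormal range loses the high/normal/low table, and the grade table cannot register the remaining part. Platelets and eosinophils, with no grade at all, keep a normal-to-high shift, while glucose does not have one below 200 mg/dL. Having a grade thus reduces coverage, which is unlikely to be intended.

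At stake is the by-arm count of subjects who moved from normal to high. A moderate rise in glucose in a minority of subjects is what a shift table is meant to show and what by-visit means can dilute. Here the table would show those subjects as unchanged, and a reader could take that as evidence of no shift.

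**Working it through.** The plan states no figure to reproduce, so the check is to run the 9.8 grades through the 5.14.5 rule.

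**Step 1. Coverage of each test**

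| Test | Graded when low | Graded when high | Abnormal region without a grade | High/normal/low table (literal reading) |
|---|---|---|---|---|
| Glucose | Grades 1-4 | Only above 200 mg/dL | Above ULN, up to and including 200 mg/dL | No |
| Hemoglobin | Grades 1-3 | No | Everything above ULN | No |
| Neutrophils | Grades 1-4 | No | Everything above ULN | No |
| Platelets, eosinophils | No | No | All | Yes |

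**Step 2. Trial values.** The documents give no reference ranges, so these are assumed: glucose LLN 70 and ULN 99, 110 or 140 mg/dL; hemoglobin LLN 12 and ULN 15.5 or 17.5 g/dL; neutrophils LLN 1800 and ULN 7000 or 8000/mm3.

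- Glucose just above each ULN (100, 111 and 141 mg/dL respectively), and at 150, 180 and 200 mg/dL: status high, grade 0 under all three ULNs. The first graded value tried is 201 mg/dL, Grade 1.
- Hemoglobin up to 4.5 g/dL above the ULN (20.0 and 22.0 g/dL): status high, grade 0.
- Neutrophils up to 20,000/mm3: status high, grade 0.

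**Step 3. What the grade table records.** Change = post-baseline grade minus baseline grade.

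- Glucose 90 to 190 mg/dL: 0 - 0 = 0. Not a treatment-emergent toxicity, and indistinguishable from a subject who stayed at 90.
- Glucose 90 to 201 mg/dL: 1 - 0 = 1. Counted.

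The glucose result holds for any ULN below 200 mg/dL, and the hemoglobin and neutrophil results for any ULN, so the assumed ranges do not drive the conclusion.

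**Step 4. The two readings of the condition.** The sentence in 5.14.5 speaks of parameters and of each laboratory test. Read that way, all three tests are excluded from the high/normal/low table. If a grade is instead taken as undefined for each direction separately, high hemoglobin and high neutrophils are undefined and come back into that table. High glucose does not, because a high grade exists. The glucose gap therefore survives both readings.

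**Step 5. With the high/normal/low shift added.** Glucose 90 to 190 mg/dL becomes a normal-to-high shift under each of the three assumed ULNs.

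**The case against.** The case for leaving the text alone has real weight.

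- **Other outputs show these values.** SAP 5.14.5 flags each quantitative hematology and chemistry result as low, normal or high, lists results with their range status, and summarizes selected quantitative tests by arm and visit. Protocol 10.2 requires clinically significant laboratory abnormalities to be reported as adverse events, and SAP 5.14.1 tabulates those by arm. This stands, with two limits: the by-visit summaries cover only selected tests, and the adverse event route depends on investigator judgement.
- **Related tests give partial cover.** SAP 9.8 assigns a grade to WBC above 11,000/mm3, which would catch some neutrophil rises. RBC count and hematocrit are required by Protocol 10.2 and do not appear in 9.8, so they keep their high/normal/low shift and would be expected to move with hemoglobin. This also stands. Neither helps glucose.
- **The exclusion is implied, and two of the three examples depend on how it is read.** Correct: hemoglobin and neutrophils are affected only on the literal reading.
- **No known signal.** Protocol 2.3 reports no notable laboratory differences from placebo in earlier trials. That limits the importance of the point but does not justify the gap.

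Stronger readings are tempting but unsupported. A reader might infer that a moderate drug effect on these tests would leave the categorical safety tables empty. It would not: affected subjects are counted in the grade table, only as unchanged, and the adverse event tables remain. A reader might also want the share of high glucose results that fall in the gap. The documents give no glucose distribution, reference range or fasting status, so any percentage would only describe assumptions.

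**Conclusion.** The point holds as a minor gap in the safety tabulations. For glucose it holds on either reading of 5.14.5, provided only that the ULN is below 200 mg/dL: a shift from normal to a value in that interval is counted as no change in grade and appears as a shift in neither table. For hemoglobin and neutrophils above the ULN it holds on the literal, test-by-test reading and disappears on a by-direction reading.

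The size is qualitative. No data are lost, no efficacy result is touched, and the other outputs give partial cover. What is missing is the by-arm count of normal-to-high shifts for tests whose grades stop short of the normal limit.

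Nor do the documents show that the 200 mg/dL grade is a mistake. It is an openly declared departure from the CTCAE row. The gap arises from the 5.14.5 condition, which makes that grade the only categorical view of high glucose.

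**What to change.** Amend SAP 5.14.5 so that the grade shift and the high/normal/low shift are no longer alternatives. The minimum is to add the high/normal/low shift (baseline to the highest and to the lowest post-baseline value) for every graded hematology and chemistry test whose grades leave part of the out-of-range region uncovered in either direction. The simpler version needs no list of tests: *In addition to any grade shift, a shift in low/normal/high status from baseline to the highest and to the lowest post-baseline result will be produced for all quantitative tests.*

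Either version closes the glucose gap, removes the ambiguity for hemoglobin and neutrophils, and covers other partly graded tests, such as WBC between the ULN and 11,000/mm3 where the laboratory's ULN is lower than that. The 200 mg/dL grade and the rest of 9.8 can stay.

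The cost is one SAP sentence and a few more standard tables, built from flags that 5.14.5 already derives. No new data are needed.

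### SAP 9.8: the hypokalemia grading bullets put exactly 3.0 mmol/L in both Grade 1 and Grade 3 and leave exactly 2.5 mmol/L ungraded, against the CTCAE row printed above them

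*SAP*

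**What the plan says.** For potassium, SAP Section 9.8 gives two statements of the hypokalemia grades.

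- **CTCAE row.** Grade 1 is "<LLN - 3.0 mmol/L", Grade 3 is "<3.0 - 2.5 mmol/L; hospitalization indicated", and Grade 4 is "<2.5 mmol/L; life-threatening consequences". Grade 2 covers the same range as Grade 1 but needs symptoms.
- **Bullets for programming.** The lead-in drops Grade 2: "Hypokalemia will have grades 1, 3, and 4". The bullets are then "Grade 1 being any values from the LLN to 3.0 mmol/L", "Grade 3 from >2.5 to 3.0 mmol/L" and "Grade 4 <2.5 mmol/L".

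The grades are used in two places. Section 3.2.4.1 defines a treatment-emergent laboratory toxicity as a rise of at least one grade over baseline. Section 5.14.5 tabulates the result: "Shift table will be used to summarize shifts from baseline toxicity grades to greatest (worst) treatment-emergent laboratory toxicity grade". Potassium is a required chemistry test (Protocol Section 10.2, Table 11).

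**The concern.** A grading rule should give every result below the lower limit of normal (LLN) exactly one grade. The hypokalemia bullets do not. They also contradict the row they are meant to implement, and nothing elsewhere in the SAP settles which of the two governs.

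At stake is how a potassium of exactly 3.0 or exactly 2.5 mmol/L enters the graded safety summaries. A 3.0 has two candidate grades. A 2.5 has none, although 2.6 is Grade 3 and 2.4 is Grade 4. The high/normal/low shift table in Section 5.14.5 is no fallback, because it is reserved for parameters without a defined toxicity grade.

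**Working it through.** No power or sample size figure is involved. The check is to write both statements as intervals and compare them.

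**Inputs (SAP Section 9.8, potassium K in mmol/L)**

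| Grade | CTCAE row | Bullets |
|---|---|---|
| 1 | 3.0 ≤ K < LLN | 3.0 ≤ K < LLN |
| 3 | 2.5 ≤ K < 3.0 | 2.5 < K ≤ 3.0 |
| 4 | K < 2.5 | K < 2.5 |

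The documents give no LLN. I took 3.5 as an assumption; any LLN above 3.0 gives the same answer at the two boundaries. The Grade 1 bullet carries no less-than sign at the LLN. I coded it as strictly below the LLN, and this choice does not affect 3.0 or 2.5.

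**Is 3.0 included in the Grade 3 bullet?** The section's own usage says yes. For hyperkalemia, Grade 2 runs from >5.5 to 6.0 and Grade 3 starts at >6.0, so the figure after the word *to* belongs to the lower grade. Where a low-direction rule excludes its upper bound, the SAP writes the less-than sign: 120 to <125 for sodium, 0.7 to <0.9 for magnesium, 6.0 to <7.0 for calcium, 30 to <40 for glucose. The hypokalemia Grade 3 bullet instead has the form used for high-direction rules.

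**Result.** Grading each value from 2.00 to 3.49 in steps of 0.01 (150 values) gives 148 agreements and 2 disagreements. Around the boundaries:

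| K | Row | Bullets |
|---|---|---|
| 2.4 | 4 | 4 |
| 2.5 | 3 | none |
| 2.6 | 3 | 3 |
| 2.9 | 3 | 3 |
| 3.0 | 1 | 1 and 3 |
| 3.1 | 1 | 1 |

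**Alternative reading.** If the 3.0 in the Grade 3 bullet is taken as excluded, the overlap disappears. The gap at 2.5 and its conflict with the row remain.

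**After the correction.** With Grade 3 as 2.5 ≤ K < 3.0, the value 3.0 is Grade 1 only, 2.5 is Grade 3 only, and every value below the LLN has one grade.

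**The case against.** The case on the other side accepts the textual conflict and disputes its consequences. Much of it stands.

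- **A reader might infer that 3.0 will be reported as Grade 3 because the shift table uses the worst grade.** Section 5.14.5 does not support that. Its wording most naturally means the worst grade across a subject's post-baseline results. It is not a rule for one result that meets two grades. The SAP has no such rule, so the outcome depends on how the conditions are programmed. Grade 3 is possible, not stated.
- **A reader might infer that 2.5 disappears from safety reporting.** It does not. It would still be flagged low against the central laboratory range and listed (Section 5.14.5), and it would still meet the separate definition of a treatment-emergent abnormality (Section 3.2.4.1). If clinically significant, it must be reported as an adverse event (Protocol Section 10.2). The loss is confined to the toxicity grading. Even there, a subject with a 2.5 at one visit may be graded from another visit.
- **Existing controls help.** The row stands directly above the bullets, Section 5.14.5 refers to CTCAE Version 5.0, and Section 9.4 requires verification by independent programming. That may expose a result with two grades or none. It does not correct the text: two programmers could both follow the faulty bullet, or resolve the tie differently while each follows the SAP.

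A deliberate departure from CTCAE is unlikely. Where the section simplifies CTCAE it says so, as in dropping Grade 2 here or grading transaminases on the ULN only. No note covers these boundaries.

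**Conclusion.** Wrong as written, and minor. The hypokalemia bullets and the CTCAE row in Section 9.8 disagree at 3.0 and 2.5 mmol/L and at no other value checked. At 3.0 the grade is ambiguous between 1 and 3, which are neighbouring categories here because Grade 2 is not used. At 2.5 a result that the row makes Grade 3 receives no grade.

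The overlap at 3.0 rests on reading the upper bound as inclusive, which is the section's own convention. The gap at 2.5 does not depend on that reading. The practical effect depends on how often results equal these values exactly. The documents give neither the reporting precision for potassium nor its expected distribution, so the number of subjects affected cannot be stated. If results are reported to one decimal (an assumption), both values can occur. No efficacy analysis uses these grades.

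**What to change.** Reconcile the Grade 3 bullet with the SAP's own row by writing it as: Grade 3 from 2.5 to <3.0 mmol/L. Leave the Grade 1 and Grade 4 bullets as written; neither needs to change to remove the overlap or the gap.

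The cost is one line in the appendix and the matching line in the grading program. If it is made before database lock and unblinding, there is no deviation to record. After that, Section 6 would require the change to be documented in the clinical study report.
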